	8.3.2 Analysis of safety outcomes	
	8.3.3 Interim analysis	
9	STUDY COORDINATION	41
RE	FERENCES	42
LI	ST OF APPENDICES	48
Αp	pendix A Detailed Study Safety Parameters	49
-	pendix B Administrative Procedures for the Reporting of A	
	pendix C Excluded Medications and Dosing Modifications	_
$\boldsymbol{\neg} \boldsymbol{\nu}$	DENDIA E EXCIDUED MEDICALIONS AND DOSING MODIFICACIONS	

PROTOCOL SYNOPSIS

TITLE: COVFIS-HOME: A PHASE 2 PLACEBO-CONTROLLED PILOT STUDY IN COVID-19 OF FISETIN TO ALLEVIATE DYSFUNCTION AND DECREASE COMPLICATIONS IN AT-RISK OUTPATIENTS

INDICATION: Reduction of complications in patients with COVID-19 infection.

OBJECTIVES: The primary objective of this study is to determine whether short-term treatment with Fisetin reduces the rate of death and long-term complications related to COVID-19. The secondary objective is to determine the safety of treatment with Fisetin in this patient population. The exploratory objective is to evaluate links between aging biomarkers and treatment effects.

PATIENT POPULATION: Males and females, at least 18 years of age, who have been diagnosed with a COVID-19 infection and have at least one high-risk criterion.

Inclusion Criteria:

- Males and females, at least 18 years of age, capable and willing to provide informed consent;
- Patient must have received a diagnosis of COVID-19 infection within the last 10 days;
- Outpatient setting (not currently hospitalized);
- Patient must possess at least one of the following high-risk criteria: 60 years or more of age, obesity (BMI ≥ 30 kg/m²), diabetes mellitus, uncontrolled hypertension (systolic blood pressure ≥150 mm Hg), known respiratory disease (including asthma, chronic obstructive pulmonary disease, or present or past smoking), known heart failure, known coronary disease, fever of ≥38.4°C within the last 48 hours, dyspnea at the time of presentation, the combination of high neutrophil count and low lymphocyte count;
- Female patient is either not of childbearing potential, defined as postmenopausal for at least 1 year or surgically sterile, or is of childbearing potential and practicing at least one method of contraception and preferably two complementary forms of contraception including a barrier method (e.g. male or female condoms, spermicides, sponges, foams, jellies, diaphragm, intrauterine device (IUD)) throughout the study and for 30 days after study completion;
- Patient or their caregiver must be able and willing to comply with the requirements of this study protocol.

Exclusion Criteria:

- Patient currently hospitalized or under immediate consideration for hospitalization;
- Patient currently in shock or with hemodynamic instability;
- Patient with severe hepatic disease (as *per* clinical judgement) or liver enzymes >2x the upper limit of normal;
- Female patient who is pregnant, breast-feeding, or is considering becoming pregnant during the study or for 1 day after the last dose of study medication;
- Patient currently taking Sirolimus, Tacrolimus, or other mTOR inhibitors for other indications (mainly chronic indications represented by organ transplantation or autoimmune diseases);
- On Warfarin therapy; Subjects taking any of the medications listed in Appendix C may participate if they are otherwise eligible AND the medication can be safely held during the following times:

- o Immediately before the 1st IP administration (Day 0) until at least 10 hours after the 2nd IP administration (Day 1)
- o Immediately before the 3rd IP administration (Day 8) until at least 10 hours after the 4th IP administration (Day 9)
- Patient with a history of an allergic reaction or significant sensitivity to Fisetin;
- Patient undergoing chemotherapy for cancer;
- Patient is considered by the investigator, for any reason, to be an unsuitable study candidate.
- History of diverticulitis or diverticulosis with GI bleeding, as per clinical judgement.

STUDY DESIGN: This will be a randomized, double-blind, placebo-controlled study. Following signature of the informed consent form, approximately 300 subjects meeting all inclusion and no exclusion criteria will be consented with a goal of randomizing 150 subjects to receive either Fisetin or placebo (1:1 allocation ratio) on Days 0 and 1 and 8 and 9 (4 doses over 10 days). Follow-up phone contacts will occur at 15 and 30 days following randomization for evaluation of the occurrence of any trial endpoints or other adverse events, with unblended follow-up contacts at Days 60.

OUTCOMES: The primary endpoint will be the rate of complications related to COVID-19 (CoV) disease using a 7 point score adapted from the WHO Ordinal Scale for Clinical Improvement of CoV (Appendix A) in the 30 days following randomization. The secondary endpoint is to determine safety and tolerability of treatment with Fisetin in this patient population. Exploratory objectives are to evaluate links between soluble and genetic markers of senescent cell abundance, SASP factors, inflammation, viral load, and treatment effects and if Fisetin treatment during acute CoV infection decreases Long-hauler syndrome at Days 60.

STATISTICAL RATIONALE AND ANALYSIS: All main analyses in COVFIS-HOME will be conducted on an intention-to-treat basis. Assuming 75 subjects/ group with a significance level of 0.05, the study will have 80% power to detect an odds ratio of 2.24 comparing the placebo- to Fisetintreated group, using the 7-point severity score at Day 30 as the endpoint in an ordinal logistic regression model.

A fully independent 5-member Data and Safety Monitoring Board (DSMB) will be established and will review unblinded safety data as detailed in the DSMB charter. An interim analysis is planned after approximately 50% of randomized patients have completed 30 days of follow-up.

The DSMB charter will pre-specify the methods of interim efficacy analyses and the rules for early study termination, approved by all board members. The stopping rules for efficacy will be based on the O'Brien-Fleming α -spending function or on a similar conservative approach so that the impact on the final alpha level will be negligible. Futility will be assessed by computing conditional power. The DSMB will have the option of recommending early study termination because of overwhelming efficacy, early termination for futility, or continuation of the trial as planned.

The primary analysis of efficacy will be based on the intent-to-treat principle. The primary endpoint will be compared between the two treatment groups using a chi-square test. Secondary endpoints will be analyzed similarly.

ANTICIPATED TOTAL NUMBER OF RANDOMIZED PATIENTS: Approximately 150 patients in total will be randomized in this study.

STUDY LOCATION: Mayo Clinic Minnesota.

GLOSSARY

AE Adverse Event/Adverse Experience

AFFIRM Alleviation by Fisetin of Frailty, Inflammation, and Related Measures Trial

ALT Alanine Aminotransferase

ARDS Acute Respiratory Distress Syndrome

AST Aspartate Aminotransferase

BAP Biospecimens Accessioning and Processing Laboratory

CFR Code of Federal Regulations

CK Creatine Kinase
CoV Coronavirus-19
CRF Case Report Form

CTCAE Common Terminology Criteria for Adverse Events

CVA Cerebrovascular Accident

D Dasatinib

DAMP Damage-Associated Molecular Profile
DSMB Data and Safety Monitoring Board
ECMO Extra-Corporeal Membrane Oxygenation
eGFR Estimated Glomerular Filtration Rate

eGFR Estimated Glomerular Filtration R ESR Erythrocyte Sedimentation Rate FDA Food and Drug Administration γ -H2.AX γ -Histone 2.A DNA Damage Foci

GCP Good Clinical Practice

GCSF Granulocyte Colony Stimulating Factor

GMP Good Manufacturing Practice

HIPAA Health Insurance Portability and Accountability Act

HUVEC Human Umbilical Vein Endothelial Cell

IB Investigator's Brochure

IL (e.g., IL-6) Interleukin (e.g., Interleukin-6)

IND Investigational New Drug Application

IP Investigational Product

IPF Idiopathic Pulmonary Fibrosis IRB Institutional Review Board

LAR Legally Authorized Representative

LPS Lipopolysaccharide

MCP-1 Monocyte Chemoattractant Protein-1

MHV Mouse Hepatitis Virus, a Mouse β-Coronavirus

MIP1-α Macrophage Inflammatory Protein 1-α

miRNA Micro-RNA

MMP Matrix Metallopeptidase
MSC Mesenchymal Stem Cell
NME Normal Microbial Experience

PAMP Pathogen-Associated Molecular Profile

PHI Protected Health Information

PI Principal Investigator

Q Quercetin

COVFIS-HOME: **COVID-**19 PILOT STUDY OF **FIS**ETIN TO ALLEVIATE DYSFUNCTION AND DECREASE COMPLICATIONS Version 4.0, 18NOV2021

SA-βGal Senescence-Associated β-Galactosidase

SAE Serious Adverse Event/Serious Adverse Experience

SASP Senescence-Associated Secretory Phenotype SCAP Senescent Cell Anti-Apoptotic Pathway

sHLH Secondary Hemophagocytic Lymphohistiocytosis

SOP Standard Operating Procedure

TAF Telomere-Associated DNA Damage Foci

TNF-α Tumor Necrosis Factor-α U of M University of Minnesota

UPIRSTO Unanticipated Problems Involving Risk to Subjects or Others

WCBP Women of Childbearing Potential

TIME PERIOD AND NUMBER OF PATIENTS:

- A. Anticipated Starting Date of Study: 1Q21
- B. Anticipated Completion Date: 4Q22
- C. Anticipated Number of Patients per Site: Centralized recruitment and follow-up
- D. Anticipated Number of Sites: Mayo Clinic Minnesota. Centralized recruitment and follow-up.

Generic Name	Strength and Dosage Form	Therapeutic Classification		
Fisetin	100 mg capsules, 20 mg/kg body weight/ day, as intact capsules or opened with powder mixed into room temperature or chilled drinks or food (e.g., pudding, apple sauce, rice pudding)	Senolytic		
	Placebo to match 100 mg capsules	NA		

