3 STUDY DESIGN

This will be an enterprise wide, randomized, double-blind, placebo-controlled study. Following signature of the informed consent form, approximately 150 subjects meeting all inclusion and no exclusion criteria will be randomized to receive either Fisetin or placebo (1:1 allocation ratio) for days 0 and 1 AND days 8 and 9. Follow-up phone assessments will occur at 15, 30, and 60 days following randomization for evaluation of the occurrence of any trial endpoints or other adverse events. Exploratory objectives are to evaluate links between soluble and genetic markers of senescent cell abundance, SASP factors, inflammation, viral load, and treatment effects and if Fisetin treatment during acute CoV infection decreases Long-hauler syndrome at Days 60.

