3.4 Active Treatment Period

All patients will receive study medication dosing (either Fisetin 100 mg or matching placebo) (PO) ON day 0 and 1 And Day 8 and 9. If a dose is missed, it should not be replaced. Throughout the study, patients will undergo phone visits (at 15, 30, and 60 days) to assess for potential study endpoints and other adverse events (AEs). Patients will be dispensed the entire supply of study medication on Day 0 to use for the duration of the study.

At each phone contact, patients will be:

- 1) questioned in a non-specific manner for the occurrence of AEs and any change in concomitant medications
- 2) 7 point score adapted from the WHO Ordinal Scale for Clinical Improvement of CoV.

Fecal, urine and buccal swab samples for biomarker are optional for the participants. The informed consent form will reflect this option and patients will specifically be asked to consent to this biomarker evaluation.

Please refer to Table 1 and Appendix A for Timetable of Visits and Requirements.

COVFIS-HOME: COVID-19 PILOT STUDY OF FISETIN TO ALLEVIATE DYSFUNCTION AND DECREASE COMPLICATIONS Version 4.0, 18NOV2021

Table 1 Timetable of Visits and Requirements

Visits	1 Screening/Ra ndomization Phone call	2 ^a Randomization/ Baseline Phone call		3 ^b Phone contact		4b Phone contact	5 ^b Phone contact	6 ^b Phone contact
Days		0	1	8 (-/+ 2 days ^d)	9	15 (-/+ 2 days)	30 (-2/+7 days)	60 (-/+ 14 days)
Informed consent	X					· · ·	V	• /
Medical/Surgical history	X							
Review Concomitant Medications	X	X		X		X	X	X
Phone contact	X	X		X		X	X	X
Review Inclusion/Exclusion criteria	X	X						
Urine pregnancy test (only women of childbearing potential)		X		X				
Randomization		X						
SF-36 Health Survey		X		X		X	X	X
Buccal, fecal and urine sample for biomarkers (optional)		X				X	X	Х
Record potential study endpoints (ordinal scale)		X		X		X	X	X
Review Adverse Events		X		X		X	X	X
Study medication dispensing		X						
Study medication dosing		X	X	X	X			

a) Screening Visit 1 and Visit 2 may be performed on the same day; under these circumstances, requirements at both Screening Visit 1 and Visit 2 will be performed once.

b) Phone contact

c) Saliva sample for pharmacogenomics evaluation will be collected using saliva collection kit.

d) Phone contact can occur + or - 2 days; however study drug administration should still occur on days 8 and 9.

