5.2.1 Adverse Event Reporting

Information regarding AEs will be collected from the first dose of study medication (at Visit 2) through and including the last visit. Any AEs prior to randomization will be recorded in the medical history and kept in the patients' chart.

In addition to standard reporting of Serious Adverse Events (SAEs) as defined and outlined in Section 5.2.1.1 below, information regarding SAEs that occur within 30 days following the last study visit, and reported to the investigational site, will be collected. Each patient will be observed and queried in a non-specific fashion at each visit during the study for any new or continuing symptoms since the previous visit.

All SAEs will be recorded on the appropriate eCRF section. The only other AEs to be recorded on the eCRF are those that are either related to the gastrointestinal system, that are judged related to the study medication by the investigator or laboratory abnormalities judged clinically significant by the investigator. Information collected will include the onset, duration, severity, relationship to study drug, and the management as outlined in Appendix C.

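### The synopsis sets the Day 60 contacts apart as 'unblended' in a double-blind study, while the body treats Day 60 like every other contact and provides no unblinding step; the two must be reconciled

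*Combined protocol and SAP*

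**What the plan says.** The Study Design paragraph of the synopsis opens: "This will be a randomized, double-blind, placebo-controlled study". It then lists the Day 15 and Day 30 phone contacts without any remark on blinding and adds a separate phrase for the last one: "with unblended follow-up contacts at Days 60".

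Section 3 repeats the declaration ("This will be an enterprise wide, randomized, double-blind, placebo-controlled study") but puts the three contacts in one list: "Follow-up phone assessments will occur at 15, 30, and 60 days following randomization for evaluation of the occurrence of any trial endpoints". Section 3.4 does the same: "patients will undergo phone visits (at 15, 30, and 60 days) to assess for potential study endpoints and other adverse events". Table 1 and Appendix A schedule the SF-36, ordinal score, adverse event review and optional samples at Day 60 just as at Days 15 and 30. Table 1 also has a concomitant medication review at all three. Section 5.4 ends the study at the last patient's Day 60 contact and mentions no release of allocation.

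Unblinded access is provided for in two places only: the code break for a patient's medical care (Section 5.2.1.1) and the DSMB's review (synopsis and Section 8.2.3).

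Day 60 has its own research question. The synopsis Outcomes paragraph and Section 3 ask "if Fisetin treatment during acute CoV infection decreases Long-hauler syndrome at Days 60", as an exploratory objective. The population description in Section 1.1 instead lists long-hauler assessment as a secondary outcome, and the primary objective in the synopsis includes long-term complications.

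**The concern.** The word 'unblended' has no sensible meaning for a phone call, and the sentence contrasts Day 60 with Days 15 and 30. A site reader could well take it as an instruction that the blind is lifted for the Day 60 contact. Nothing in the body confirms that, and nothing says expressly that the blind is kept through Day 60.

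What is at stake is the Day 60 information. Long-hauler symptoms and the SF-36 are reported by the patient, and the ordinal score is taken by phone, so all are open to expectation once the arm is known. Under Section 5.2.1, serious events, gastrointestinal events and clinically significant laboratory abnormalities are recorded whatever their cause. Other non-serious events reach the eCRF only if the investigator judges them related to study medication. Knowledge of the arm could therefore affect which of those events are recorded at all. The medication review and the optional samples are less exposed.

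**Working it through.** There is no figure in the plan to reproduce. The check is a comparison of the text plus arithmetic on the visit windows.

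**Text comparison**
- Synopsis, Study Design: double-blind; Days 15 and 30 unqualified; Day 60 given its own, different label.
- Sections 3 and 3.4, Table 1, Appendix A: Day 60 grouped with the other contacts; no blinding status given for any single contact.
- Section 5.4: study ends at the last Day 60 contact; no unblinding step.
- Sections 5.2.1.1 and 8.2.3: the only unblinding routes, neither tied to Day 60.
- Nowhere stated: who would be unblinded at Day 60, or whether before, during or after the assessments.

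**Windows (Table 1 and Appendix A)**
- Day 30 contact: 30 − 2 = Day 28 to 30 + 7 = Day 37.
- Day 60 contact: 60 − 14 = Day 46 to 60 + 14 = Day 74.

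**Adverse event period asked about at Day 60.** Section 5.2.1 has patients "queried in a non-specific fashion at each visit during the study for any new or continuing symptoms since the previous visit", so the interval runs from the Day 30 contact to the Day 60 contact.
- Nominal: 60 − 30 = 30 days, that is 30 of the 60 days of follow-up.
- Shortest: 46 − 37 = 9 days.
- Longest: 74 − 28 = 46 days.

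**Same patient's Day 30 assessment.** The smallest gap before the Day 60 contact is 46 − 37 = 9 days. If the Day 30 call is made in its window and allocation is released no earlier than the Day 60 contact, that assessment comes first.

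**Other patients.** Take two patients, the second randomized *t* days after the first. The second patient's Day 30 assessment falls after the first patient's Day 60 contact when *t* + 30 > 60, so *t* > 30 days at nominal timing. By the windows, the threshold lies between 46 − 37 = 9 and 74 − 28 = 46 days. The synopsis-level timetable runs from 1Q21 to 4Q22 with centralized recruitment and follow-up, so many such pairs are to be expected. Patient-by-patient unblinding could then make allocations known to staff who have yet to assess others at Day 30. One patient's allocation does not disclose another's; the route is indirect, through impressions or guesses formed from known cases.

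**The case against.** The strongest reply is that this is one odd word in a synopsis set against a consistent body. Both design statements say double-blind, the body gives Day 60 no special status, and Section 5.4 still speaks of double-blind medication when it defines completion. The document has other leftovers: Section 1.5 describes subjects as hospitalized in what is an outpatient trial. The word may be a drafting remnant. Even read as 'unblinded', it could mean disclosure at the end of the call, which would leave that call's answers blinded. Lifting the blind after a 30-day endpoint can also be a legitimate choice, and dosing ends on Day 9.

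Most of this stands. It rules out a stronger reading that a reader might infer, namely that the protocol plans an open-label Day 60 phase. The documents show a mismatch and an inferred word, not a decision. It also means the Day 60 data *could*, not *would*, be open-label.

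The reply does not remove the point. Whether the word is a slip for 'blinded' or for 'unblinded', the synopsis needs correcting, and no passage settles the matter for staff.

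**Conclusion.** The inconsistency is real and worth correcting, on the footing that 'unblended' most plausibly means 'unblinded'. If followed, it could leave the Day 60 long-hauler comparison, SF-36, ordinal score and relatedness-dependent adverse event recording open to expectation bias. It would be wrong to call all of this merely exploratory, because Section 1.1 lists long-hauler assessment as secondary and the synopsis primary objective includes long-term complications.

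The size of any bias cannot be given: the plan names no specific Day 60 test, and the 9-to-46-day range describes the period the contact covers, not an effect.

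A reader might also infer that the 30-day primary endpoint is compromised. The documents do not support that as a direct effect, since a patient's own Day 30 assessment, done by Day 37, precedes a Day 60 contact from Day 46. Two qualifications remain. Sections 3 and 3.4 also use the Day 60 contact to look for endpoints, so an early event missed before could first surface there. Staff who learn earlier patients' allocations may still be assessing later patients. Serious event recording does not depend on relatedness and is not affected by that route.

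**What to change.** Reconcile the synopsis with the body.

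- In the synopsis, replace the phrase with: *with blinded follow-up contacts at Day 60*.
- In Sections 3 and 5.4, add: *Patients, callers and investigators stay blinded until the last patient's Day 60 contact is complete and the database is locked, except for code breaks under Section 5.2.1.1 and DSMB review.*

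This also closes the route through staff who are still following other patients.

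If the sponsor did intend open Day 60 contacts and keeps them, Section 3 should state who is unblinded and when, keep unblinded staff away from assessing patients who have not completed follow-up, and have the Day 60 data reported as open-label.

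Cost: text edits only if the word is a slip. If open contacts were intended, patients learn their assignment later, and any consent wording on this would have to match (the consent pages are not available here).

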1 INTRODUCTION

1.1 Background

Coronavirus-19 (CoV): Coronaviruses constitute the subfamily *Orthocoronavirinae*, in the family *Coronaviridae*, order *Nidovirales*, and realm *Riboviria*. They are enveloped viruses with a positive-sense single-stranded RNA genome and a nucleocapsid of helical symmetry. They are the largest among known RNA viruses. As of May 5, 2020, there have been at least 25,486 confirmed deaths and more than 3,646,206 confirmed cases in the β-coronavirus-19 (CoV) pandemic. CoV can cause physical dysfunction (frailty) and death from hyper-inflammation, cytokine storm, and associated acute respiratory distress syndrome (ARDS) and myocarditis with troponin leak, particularly in older or chronically-ill individuals⁸. Mouse hepatitis virus (MHV) is a β-coronavirus that is related to CoV, which causes an epidemic murine illness with high mortality, especially among colonies of laboratory mice⁹. We previously found that cellular senescence leads to physical dysfunction (frailty) and hyper-inflammation (cytokine storm), factors that contribute to morbidity and mortality from CoV. We are currently conducting a clinical trial of Fisetin in elderly subjects for these indications, AFFIRM (Alleviation by Fisetin of Frailty, Inflammation, and Related Measures in Older Adults; ClinicalTrials.gov identifier NCT03430037; IND 134052).

Longhauler Syndrome: Initial reports from WHO-China in February described clinical recovery from time of onset of COVID symptoms to be between 2-6 weeks, the latter being patients with more severe cases (https://www.who.int/docs/default-source/coronaviruse/situation-reports/20200306-sitrep-46-covid-19.pdf?sfvrsn=96b04adf 4). As more information becomes available, patients are coming forward with experiences of longer recovery times and lingering symptoms, Long Covid, Long-haul Covid, or Long-haulers¹⁰⁻¹². Though largely undefined, "Long-haulers" denotes patients who experience persistent symptoms after having acute COVID-19. While the full impact of long COVID is widely unknown, some sources are reporting upwards of 10% of patients experiencing symptoms lasting greater than 3 weeks¹². An earlier study done in Italy showed that 87% of hospitalized patients reported at least one ongoing symptom 60 days after onset of first COVID-19 symptoms, with 55% of patients reporting 3 or more ongoing symptoms¹³. These long lasting symptoms can occur in adults across all age groups, regardless of pre-existing conditions¹⁴. The long term sequelae of the virus are largely unknown, but early reports of significant lung damage^{15,16} and persistent myocardial inflammation¹⁷ are concerning, making the discovery of long term impact at the mechanistic level all the more urgent.

Cellular Senescence: Cellular senescence contributes to age-related dysfunction and multiple diseases throughout the lifespan. Senescent cell burden is very low in young individuals but increases with aging in several tissues. These include adipose tissue, skeletal muscle, heart, kidney, brain, bone, and skin^{5,18-24}. Senescent cells accumulate at sites of pathology in multiple chronic diseases, including, among others, the lungs in chronic obstructive pulmonary disease, asthma, idiopathic pulmonary fibrosis (IPF), and smoking, adipose and other tissues in diabetes/ obesity, the brain in Alzheimer's and other dementias, and blood vessels and the heart in cardiovascular disease.

Senescent cells were discovered in 1961²⁵ when serially-subcultured human embryonic fibroblasts were shown to lose replicative capacity, yet remain viable. This prompted work to test if aging leads to accumulation *in vivo* of pre-senescent cells, which have limited remaining replicative potential, and senescent cells, which cannot replicate but are metabolically active. In 1979, this was reported to be true for fibroblasts in skin biopsied from older than younger subjects⁶ and by us in 1990, for primary adipocyte progenitors (preadipocytes) cloned from adipose tissue of rats across the age

spectrum that had been raised under controlled conditions⁷. Senescent cells appear at pathogenic sites of many major diseases, including chronic lung disease, diabetes/ obesity, cardiovascular diseases, Alzheimer's disease, cancers, osteoporosis, renal disease, and cirrhosis in preclinical species and humans^{5,21,23}, conditions associated with physical dysfunction (frailty), inflammation, and CoV morbidity and mortality.

Senescence is essentially a cell fate, like differentiation, proliferation, apoptosis, or necrosis. External and internal signals can contribute to driving a cell into senescence. These are generally cell or tissue damage-related, including DNA alterations (dysfunctional telomeres, strand breaks, etc.), metabolic dysfunction (reactive oxygen species [ROS], high glucose, bioactive lipids, mitochondrial dysfunction), protein alterations (aggregates, misfolding, failed autophagy), inflammatory signals, mechanical/shear stress, pathogen-associated molecular pattern factors (PAMPs), including viruses, bacterial/fungal proteins, lipopolysaccharide (LPS), etc., damageassociated molecular pattern factors (DAMPs; tissue damage signals [extracellular nucleotides, etc.]), cellular damage signals (DNA damage, telomeric dysfunction, protein aggregates, mitochondrial dysfunction), oncogenes, and mitogens (insulin-like growth factor-1, etc.). Once initiated, senescence takes 10 days to 6 weeks to become established through transcription factor cascades (that may, but do not always, include p16^{INK4a}/ retinoblastoma protein and/or p53/p21^{CIP1}), causing extensive changes in gene expression, histone modifications, altered organelle function (e.g., mitochondria, endoplasmic reticulum, nucleolus, nuclear envelope), elevated protein production due to increased mTOR and decreased autophagy, and profound morphological and metabolic shifts^{21,26}. After drug-induced removal, senescent cells take from 10 days to 6 weeks to reoccur if cellular senescence inducers remain present, at least in vitro.

There are no fully sensitive or specific markers for identifying senescent cells. These cells are generally large, may have high $p16^{INK4a}$ and/or $p21^{CIP1}$ (but not always), and exhibit DNA damage foci, particularly in telomeres (telomere-associated DNA damage foci [TAFs]), senescence-associated distention of pericentromeric satellite DNA, and increased senescence-associated β -galactosidase $(SA-\beta Gal)^{21}$. Like cancer cells, senescent cells frequently are metabolically-shifted from fatty acid utilization toward glycolysis, resulting in ROS generation, lipid accumulation, lipotoxicity, and dysdifferentiation into adipocyte-like but insulin-resistant "MAD" (mesenchymal adipocyte-like default) cells²⁷. Senescent cells are resistant to apoptosis²⁸.

Senescent Cell Characteristics: Cellular senescence leads to inflammation, fibrosis, DNA damage, mitochondrial dysfunction, ROS generation, NAD⁺ depletion, protein aggregation, failed autophagy, lipotoxicity, and stem and progenitor cell dysfunction. In turn, cellular senescence can be caused by other fundamental aging processes, including DNA damage, low NAD⁺, mitochondrial dysfunction, ROS, protein aggregates, and lipotoxicity. Thus, from our and others' data, fundamental aging processes appear to be interlinked, findings that led us to formulate a "Unitary Theory of Fundamental Aging Processes", which posits that interventions, such as senolytics, targeting any one of these processes, such as cellular senescence, will affect many of the rest of the aging processes that predispose to aging phenotypes, frailty, hyper-inflammation, chronic diseases, and morbidity and mortality from acute insults, including viral infection. Effects of the study agent in our clinical trial will be ascertained not only on senescent cell abundance and effects, but also on these other fundamental aging processes.

Senescence-Associated Secretory Phenotype (SASP): Accumulation of senescent cells can cause local and systemic inflammation, tissue destruction, immune system inhibition, and stem and progenitor cell dysfunction due to their SASP^{3,4,21,29,30}. Generally 30-70% of senescent cells develop

a SASP that entails release of pro-inflammatory, pro-apoptotic cytokines (TNFα, IL-1α, IL-6, IL-7, IL-8, IFNγ, and many more), chemokines (*e.g.*, MCP-1, MIP1-α, RANTES, RARRES2) that attract, activate, and anchor immune cells (including macrophages, dendritic cells, T-lymphocyte subsets, and neutrophils), tissue-destroying proteases (MMP-3, -9, -12, *etc.*), pro-coagulant factors (PAI-1, *etc.*), factors that impede stem cell/ progenitor function (Activin A, TGF-β-related proteins), ferritin, growth factors (*e.g.*, GCSF), bioactive lipids (bradykines, saturated ceramides, prostanoids), micro-RNA's (miRNA's), tissue-damaging non-coding nucleotides (including release of mitochondrial DNA, which attracts, activates, and anchors dendritic cells³¹), microvesicles including exosomes, and other factors that cause tissue necrosis, systemic inflammation, stem cell/ progenitor dysfunction, and spread of senescence to non-senescent cells. These SASP factors include those that result in frailty, hyper-inflammation/ cytokine storm/ ARDS/ myocarditis with troponin leak in CoV patients⁸.

Likely due to their SASP, only a small number of senescent cells can cause considerable dysfunction. In pre-clinical experiments, transplanting senescent cells around the knee joints of young mice was sufficient to induce an osteoarthritis-like phenotype, while transplanting non-senescent cells did not³². Transplanting 10⁶ radiation- or chemotherapy-induced senescent autologous ear fibroblasts or syngeneic adipocyte progenitors intraperitoneally into lean, adult mice, so that fewer than 1/10,000 of all cells in the transplanted mice were senescent, induced impaired physical function (frailty) and premature death due to early onset of the same age-related diseases that cause death in naturally-aged mice³². This also occurred after human senescent (*vs.* non-senescent) cells were transplanted into immune-deficient (SCID) mice. When labelled senescent cells are transplanted intraperitoneally, they remained within the peritoneum, yet the transplant recipients developed non-labeled senescent cells in their limbs, demonstrating that senescence can spread from cell to cell, even at a distance³².

We established that adipose tissue from obese individuals have an increased burden of senescent adipocyte progenitors³³. Furthermore, these senescent cells have a potent pro-inflammatory SASP. This leads to the hypothesis that an older or obese individual or any other individual with an increased burden of senescent cells could be predisposed to frailty, hyper-inflammation/cytokine storm/ ARDS/ myocarditis with troponin leak after CoV infection.

Clearance of Senescent cells by the Immune System: Senescent cells are usually cleared by the immune system³⁴. They can attract, activate, and anchor immune cells, including macrophages, dendritic cells, T-lymphocytes, and neutrophils through such SASP chemokines as MCP-1, MIP1-α, RANTES, and RARRES2, cytokines such as IL-6, and TNFα, extracellular mitochondrial DNA, possibly miRNAs, and other factors^{31,32,34,35}. However, above a threshold burden, senescent cells interfere with the immune system and its ability to remove them. For example, IL-6, a SASP component, interferes with macrophage migration, MMPs can cleave FAS ligand and other immune cell surface proteins, senescent cells cause fibrosis (impeding immune cell infiltration and trapping immune cells within inflammatory foci), and senescent cells can express "don't eat me" signals³⁴. Consistent with this, senescent cells can drive cancer initiation and progression, which senolytics are highly effective at preventing, with substantial delays in death from multiple forms of cancer in mice^{5,32,36}. Fisetin, which selectively clears senescent cells, delays death of older mice, 50% of which die from cancer, by over 17%³⁶.

Threshold Theory of Senescent Cell Burden: Based on the above, we formulated a "Threshold Theory of Senescent Cell Burden", which holds that once senescent cell abundance is sufficient to cause spread of senescence that exceeds capacity of the immune system to keep up with clearing

these cells, an accelerated aging-like state ensues^{32,34}. Consistent with this: 1) the number of senescent cells that needs to be transplanted to cause frailty, limit healthspan, and cause premature death, including from cancer, is higher in young than old mice and in young lean than young obese mice. Old mice or young, obese mice have more pre-existing senescent cells than young, lean mice³². 2) Senescent cell abundance remains low in skin until early old age in humans, followed by an upward inflection in senescent cell burden in subjects who are in their late 60's through the mid-70's³⁷. This precedes the age-related increase in multi-morbidity³⁸. 3) The lag between induction of senescence by chemotherapy and development of age-related morbidities is longer in childhood cancer survivors than adults who received higher chemotherapy doses in preparation for bone marrow transplantation^{39,40}. These findings support the hypothesis that there is a threshold above which senescent cell burden due to spread of cellular senescence becomes self-amplifying. This causes increased risk for senescence- and age-related phenotypes, physical dysfunction/ frailty, hyper-inflammation, and diseases, perhaps contributing to age-related multi-morbidity³⁸. Potentially, attraction, activation, and anchoring of immune cells is accelerated after senescent cells exceed this threshold, predisposing to excessive inflammation in frailty and during viral infection, plus continuing and exacerbating production of the SASP factors that underlie frailty, hyperinflammation/ cytokine storm, ARDS, and cardiomyopathy, as occurs in fatal CoV cases, as well as subsequent fibrosis, e.g., of the lungs.

Pathogen-Associated Molecular Profile Factors (PAMPs): Of note, the SASP is modifiable: drugs, hormones, and especially the PAMPs associated with infections such as coronaviruses, can modify the SASP. We found that PAMPs can exacerbate the SASP in previously relatively quiescent human senescent cells by multiple fold (much greater than the effect of cytokines on the SASP), with greatly increased secretion of factors underlying cytokine storm (IL-6, IL-8, MCP-1) and increased attraction and activation of innate immune cells, potentially driving the frailty, hyperinflammation, cytokine storm, and ARDS caused by coronavirus (Fig. 1).

[figure not shown]

Fig. 1. Senescent cells challenged with PAMPs highly express SASP factor mRNAs. Human subcutaneous adipocyte progenitors from different subjects were irradiated or not to generate senescent or

proliferating cells, respectively (n=3). Then cells were treated with different concentrations of the prototype PAMP, LPS, for 3 hours before mRNA isolation. One-way ANOVA and Dunnett multiple comparison posttests were performed against the control (0 ng) for each condition (proliferating or senescent). * = p<0.05, ** = p<0.01. Human non-senescent and radiation-induced senescent preadipocytes were treated with human recombinant IL-6, TNF- α , and IFN- γ for 3h.

Similar results were obtained *in vivo* when progeroid mice, which have senescent cells to the same extent and in the same tissues as aged mice, were challenged with the PAMP, LPS (Fig. 2). In two tissues examined (kidney and liver), levels of senescence markers ($p16^{lnk4}$, $p21^{Cip1}$) and the SASP ($II1\Box$, II6, $TNF\Box\Box$ and Mcp1) were greater in the progeroid mice compared to age-matched controls, illustrating an amplification of the response to PAMPs in organisms with increased senescent cell burden. In another study focused on neuroprotection in the face of LPS challenge, rats were administered Fisetin 20 i.p. mg/kg/day x 14 days, while being challenged with LPS⁴¹. In Fisetin-treated animals, inflammation and neurodegeneration were suppressed, while memory improved.

[figure not shown]

Fig. 2. Pre-existing senescence causes an exaggerated response to pathogens *in vivo*. Eleven-week-old wild-type (blue) and progeroid $Ercc1^{-/-}$ (red) mice were injected with 500 ng/kg of LPS or vehicle (PBS) i.p. (N=4/ group). Twenty-four hours post-injection, mice were euthanized and tissues were collected. Total RNA was isolated from tissues and senescence and SASP marker expression were quantified in the (**A**) kidney and (**B**) liver by real-time qPCR using the ΔΔCt method. *Gapdh* was used as a control for gene expression analysis. (**C**) Circulating levels of IL-6 and MCP-1 were quantified in serum by ELISA. All values represent

the mean \pm SD. Statistical significance was determined by two-way ANOVA. * p<0.05, ** p<0.01, *** p<0.001, ****p<0.0001. (unpublished data, [name], [name], [name], [name]).

